11.3 Progression-Free Survival and Overall Survival Rates

PFS and OS will be assessed using the Kaplan-Meier estimate. Since we don't have enough patients on either arm for a firm comparison to the literature, we plan to simply provide descriptive statistics and projected 2-year and 5-year PFS and OS estimates for the following two arms:

- A. Definitive chemoradiation We completed an internal Phase II trial that used intensity-modulated radiation therapy (IMRT) to a dose of 60 Gy with concurrent chemotherapy. The 2-year PFS and overall survival rates (OS) from that experience are 25% (95% CI of 11 62%) and 36% (95% CI of 7 49%), respectively. These results are consistent with the literature.
- B. Neoadjuvant chemoradiation followed by esophagectomy The two-year PFS and OS rates for patients with adenocarcinoma of the esophagus or gastroesophageal junction treated with neoadjuvant chemoradiation followed by esophagectomy on CALGB 9781 was 60% and 70%, respectively (taken from PFS and OS curves). (Tepper, Krasna, Mayer et al. 2008: 26:1086)

11.4 Patient Reported Outcomes

We will calculate descriptive statistics (mean, standard deviation, etc.) for all QOL data (EQ-5D, SF-12) in addition to other PROs (depressive symptoms, social support) at each evaluation period. Univariate tests will explore the associations among QOL and PROs using analysis of variance (ANOVA) and Fisher's exact test for correlation. Changes over time in QOL and PROs will be analyzed utilizing repeated-measures modeling techniques

Protocol Version: 05/16/2023 Page 26 of 45

(repeated measures analysis of covariance).

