1.4.2 EQ-5D

The EQ-5D is a standardized 2-part, patient-administered instrument used for direct and indirect assessment of health state utilities; it is cognitively simple, takes only a few minutes to complete, and yields a utilities index value for health status (Pickard 2007). The first part asks respondents to "check the ONE box [next to the appropriate statement] that best describes your health TODAY" for each of 5 health dimensions, including mobility, self-care, usual activities, pain/discomfort, and anxiety/depression (Johnson & Coons, 1998). The second part of the EQ-5D is a visual analogue scale (VAS) valuing current health state. Both the 5-item index score and the VAS score are transformed into a utility score between 0 "Worst health state" and 1 "Best health state." For this study, we will report both the health state classification instrument and the visual analog scale (VAS) utilities. The former is considered to satisfy the "community preferences" recommendation of the Panel on Cost Effectiveness, whereas the VAS is considered to satisfy the

Protocol Version: 05/16/2023 Page 10 of 45

Panel's "patient preferences" recommendation.(Gold 1996) Over 30 published studies provide evidence to support its validity and reliability in cancer.

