1.4.3 SF-12

The 12-item SF-12 is a shorter, yet valid alternative to the SF-36 for measuring physical and mental functional status in the general population (Ware, Kosinski, Keller 1995) (Ware, Kosinski, Keller 1996). The SF-12 has well-established norms, has been extensively validated, is sensitive to changes over time, has established minimally clinically important changes, and has been used in cancer studies (Ramsey et al 2002) (Scarpa et al 2009) (Siassi et al 2009). We have experience using the SF-12 in our research (Lian, Jeffe, Schootman 2008). The SF-12 will be measured at each of 7 interviews, and mental and physical component scores will be calculated in addition to calculating the measure's eight individual subscales (physical functioning, social functioning, role limitations due to physical problems, body pain, general health, role limitations due to emotional problems general health, vitality, and mental health). Higher scores indicate better quality of life.

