1.4.4 MOS Social Support

The 19-item Medical Outcomes Study (MOS) Social Support Survey was designed for use with patients with chronic diseases and measures how often different kinds of support are available, if needed (Sherbourne, Stewart 1991). Response choices range from "none of the time" (1) to "all of the time" (5). A mean social support score for all 19 items is computed with higher scores indicating a greater availability of social support. Social isolation and lack of social support are related to increased mortality from a number of causes (Berkman et al 1993; Berkman, Syme 1979; Orth-Gomer, Johnson 1987; Kaplan et al 1998) and social support has been associated with cancer patients' QOL in previous studies (Jeffe et al 2012; Waters et al 2013). We hypothesize that lower levels of perceived social support will be associated with poorer QOL.

1.4.5 4-Item CES-D

The Center for Epidemiological Studies Depression Scale (CES-D) is a 20-item measure which evaluates depressive symptoms. This trial will make use of the validated 4-item screening version in order to reduce participant burden (Melchior et al 1993). There will be a referral plan in place for psychosocial counseling services for depressed patients. Depression has been shown to be related to QOL in other cancer patient populations (Longman et al 1996; Jeffe et al 2012). We hypothesize that depressive symptoms will be associated with poorer QOL.

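### Section 11.4 names Fisher's exact test as a correlation method and, with ANOVA, gives no cut-points for the summary scores these tests would have to group

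*Combined protocol and SAP*

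**What the plan says.** Section 11.4 (Patient Reported Outcomes) plans three things:

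- Descriptive statistics, with mean and standard deviation as the examples, "for all QOL data (EQ-5D, SF-12) in addition to other PROs (depressive symptoms, social support").
- Tests of association: "Univariate tests will explore the associations among QOL and PROs using analysis of variance (ANOVA) and Fisher's exact test for correlation".
- Changes over time, by "repeated measures analysis of covariance".

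Section 1.4 describes what is measured:

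- **SF-12 (1.4.3):** "mental and physical component scores will be calculated", together with eight subscales.
- **MOS social support (1.4.4):** "A mean social support score for all 19 items is computed".
- **EQ-5D (1.4.2):** "Both the 5-item index score and the VAS score are transformed into a utility score between 0" and 1. The health-state classification is also to be reported.
- **CES-D (1.4.5, Appendix G):** four items with four ordered answers each. It is called a screening version, but no scoring rule or threshold is given.

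Two hypotheses about associations are stated, one in 1.4.4, "We hypothesize that lower levels of perceived social support will be associated with poorer QOL", and one in 1.4.5, "We hypothesize that depressive symptoms will be associated with poorer QOL".

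**The concern.** The sentence on associations pairs an aim (correlation) with a method that does not deliver it. Fisher's exact test gives a p-value for a contingency table, and the usual effect measure beside it is an odds ratio. If Fisher's z transformation of a correlation coefficient was intended, 11.4 does not say so.

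The two hypotheses are about gradients: less support, or more depressive symptoms, going with poorer quality of life. Testing a gradient between two scores by ANOVA or Fisher's test means first cutting one or both into groups. Cutting discards information in a trial of 40 patients. It also makes the size of the reported effect depend on where the cut falls, and the plan leaves that open until after the data are in. Section 11.1 says the trial is meant to supply preliminary data for later studies. An estimate tied to an unstated cut-point is hard to carry into another study.

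**Working it through.** The plan states no alpha, effect size or power for these tests, so there is no figure to reproduce. The check has four parts.

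**1. Does each measure fit the named tests as it stands?**

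| Measure | Form in the documents | Cut-point needed? |
|---|---|---|
| MOS mean (1.4.4) | numeric, 19 items scored 1 to 5 | yes, none given |
| SF-12 component scores (1.4.3) | numeric | yes, none given |
| EQ-5D index and VAS (1.4.2) | numeric, 0 to 1 | yes, none given |
| CES-D summary (1.4.5, 11.4) | to be summarised by mean and SD | yes, none given |
| EQ-5D dimensions (Appendix C) | five ordered levels | no |
| SF-12 items 4 to 7 (Appendix E) | yes/no | no |
| CES-D items (Appendix G) | four ordered levels | no |

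The need for grouping therefore applies to the first four rows, which are the scores behind the two hypotheses. It does not apply to the last three.

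**2. What does grouping cost?** This is a simulation on assumptions that are not in the documents. X is standard normal and Y = rX + √(1 − r²)E, with E an independent standard normal. Tests are two-sided at 5%, with 20,000 replicates per cell. ANOVA splits one score at its median and Fisher's test splits both. The n of 40 is the enrolment in 11.1. The n of 30 is an assumed smaller number at a follow-up visit, because the documents give no questionnaire completion rate.

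| True r | n = 40: Spearman / ANOVA / Fisher | n = 30: Spearman / ANOVA / Fisher |
|---|---|---|
| 0.3 | 0.432 / 0.322 / 0.153 | 0.329 / 0.243 / 0.120 |
| 0.4 | 0.694 / 0.531 / 0.282 | 0.547 / 0.403 / 0.211 |
| 0.5 | 0.885 / 0.746 / 0.453 | 0.769 / 0.613 / 0.344 |
| 0.6 | 0.980 / 0.909 / 0.654 | 0.926 / 0.806 / 0.523 |

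At r = 0.4 and n = 40, ANOVA loses 0.694 − 0.531 = 0.163 of power and Fisher's test loses 0.694 − 0.282 = 0.412. At n = 30 the losses are 0.547 − 0.403 = 0.144 and 0.547 − 0.211 = 0.336.

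A skewed 0–12 CES-D total (items assumed scored 0 to 3) in place of one normal score gives the same ordering at r = 0.4: 0.723 / 0.596 / 0.287 at n = 40 and 0.593 / 0.466 / 0.192 at n = 30.

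With no association and n = 40, the rejection rates are 0.051 / 0.050 / 0.027. A median split fixed in advance does not raise the false-positive rate.

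**3. Does the place of the cut matter?** Under the same bivariate normal model with r = 0.4, the ANOVA verdict at p < 0.05 differs among cuts at the 25th, 50th and 75th percentiles in 54% of data sets at n = 40 and in 50% at n = 30.

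**4. What would a correlation report?** An approximate 95% interval for an observed Spearman coefficient of 0.4 is tanh(atanh 0.4 ± 1.96·√((1 + 0.4²/2)/(n − 3))).

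- n = 40: 0.424 ± 1.96 × √(1.08/37) = 0.424 ± 0.335, which gives 0.09 to 0.64.
- n = 30: 0.424 ± 1.96 × √(1.08/27) = 0.424 ± 0.392, which gives 0.03 to 0.67.

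The intervals are wide, but they depend on no cut-point.

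**The case against.** **Some of the data are already categorical.** EQ-5D dimensions, SF-12 yes/no items and CES-D items can go into ANOVA or a contingency table unchanged. This stands, and a claim that every patient-reported variable must be grouped would be wrong. It does not settle the matter, because 11.4 speaks of quality of life and PROs in general and summarises them by mean and standard deviation.

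**The analyses are exploratory.** This also stands. The associations are not among the objectives in Section 2, the hypotheses appear only in the background, and 11.1 disclaims power. The weight is low for that reason.

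**The repeated-measures analysis of covariance could cover the hypotheses.** It could take undivided scores as covariates. However, that sentence is about change over time, and it names no covariate.

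**Inflated false positives.** A reader might infer that the plan inflates the false-positive rate. With no association, taking the best of three cut-points gives ANOVA about 12–13%, and taking the best of nine pairs gives Fisher's test about 13–18%. Those rates need an analyst who searches over cuts, and the documents describe no such search. What they support is narrower: the cut is unstated, and the answer depends on it.

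**A correlation at every visit brings its own multiplicity.** Section 1.4 yields 2 EQ-5D scores, 2 SF-12 components and 8 subscales, or 12 scores. Against two other PROs at seven visits that is 12 × 2 × 7 = 168 correlations. This stands, and the fix has to name key pairs and visits.

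**Conclusion.** The point holds with low weight. Section 11.4 names a contingency-table test as a correlation method. For the summary scores behind the two stated hypotheses, the named tests cannot be run without cut-points, and the plan gives none. This is a method that does not match its stated purpose, and not merely a missing detail.

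Under the illustrative assumptions (r = 0.4, two-sided 5%, bivariate normal, median splits), power falls from about 0.69 with Spearman to 0.53 with ANOVA and 0.28 with Fisher's test at n = 40. At n = 30 it falls from 0.55 to 0.40 and 0.21. The exact figures move with these assumptions. The ordering is the same for every r from 0.3 to 0.6 and for a skewed CES-D.

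A reader might take this as a flaw in the primary patient-reported analysis at 6 and 12 months. The documents do not support that: those objectives rest on the descriptive statistics and the repeated-measures model, which this sentence does not affect.

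**What to change.** Replace the sentence on univariate tests in 11.4 with:

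> Associations of social support and CES-D scores with QOL scores will be estimated by Spearman correlation with 95% CIs, with the SF-12 component scores and EQ-5D index at 6 and 12 months after chemoradiation as the key pairs and all other pairs and visits descriptive; Fisher's exact test will be used only for variables that are already categorical.

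This leaves 2 × 3 × 2 = 12 key correlations: two PROs, three quality-of-life scores and two visits. The cost is one sentence, with no new data and no extra visits.

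A separate clarification, which adds no weight here, concerns MDASI-Plus. Section 1.4 counts it among the patient-reported outcomes, but the descriptive list in 11.4 does not name it or give a summary score for it. The sponsor can add both in the same edit, and the choice of score is the sponsor's.

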APPENDIX A: ECOG Performance Status Scale

Protocol Version: 05/16/2023 Page 28 of 45

Grade	Description
0	Normal activity. Fully active, able to carry on all pre-disease performance without restriction.
1	Symptoms, but ambulatory. Restricted in physically strenuous activity, but ambulatory and able to carry out work of a light or sedentary nature (e.g., light housework, office work).
2	In bed <50% of the time. Ambulatory and capable of all self-care, but unable to carry out any work activities. Up and about more than 50% of waking hours.
3	In bed >50% of the time. Capable of only limited self-care, confined to bed or chair more than 50% of waking hours.
4	100% bedridden. Completely disabled. Cannot carry on any self-care. Totally confined to bed or chair.
5	Dead.

Protocol Version: 05/16/2023 Page 29 of 45

APPENDIX B: MD Anderson Symptom Inventory (MDASI)-Plus

14032	Date: / (day)	(year)	Data collection to Assess Acute and Late Normal Tissue Sequelae in Proton Therapy for Adults Protocol: PCR05-0207
	Participant Initials:		PI: [name] Revision: 05/25/2010
PLEASE USE BLACK INK	Participant #.		Assessment Visits: Week

M. D. Anderson Symptom Inventory - Plus

Part I. How severe are your symptoms?

People with cancer frequently have symptoms that are caused by their disease or by their treatment. We ask you to rate how severe the following symptoms have been *in the last 24 hours*. Please fill in the circle below from 0 (symptom has not been present) to 10 (the symptom was as bad as you can imagine it could be) for each item.

each item.	NOT PRESENT	-								AS BAD CAN IM	AS YOU AGINE
	0	1	2	3	4	5	6	7	8	9	10
Your pain at its WORST?	0	0	0	0	0	0	0	0	0	0	0
Your fatigue (tiredness) at its WORST?	0	0	0	0	0	0	0	0	0	0	0
3. Your nausea at its WORST?	0	0	0	0	0	0	0	0	0	0	0
Your disturbed sleep at its WORST?	0	0	0	0	0	0	0	0	0	0	0
Your feeling of being distressed (upset) at its WORST?	' O	0	0	0	0	0	0	0	0	0	0
Your shortness of breath at its WORST?	0	0	0	0	0	0	0	0	0	0	0
Your problem with remembering things at its WORST?	, O	0	0	0	0	0	0	0	0	0	
Your problem with lack of apper at its WORST?	tite 🔘	0	0	0	0	0	0	0	0	0	0
Your feeling drowsy (sleepy) at its WORST?	0	0	0	0	0	0	0	0	0	0	0
10. Your having a dry mouth at its WORST?	0	0	0	0	0	0	0	0	0	0	0
11. Your feeling sad at its WORST?	0	0	0	0	0	0	0	0	0	0	0
12. Your vomiting at its WORST?	0	0	0	0	0	0	0	0	0	0	0
13. Your numbness or tingling at its WORST?	0	0	0	0	0	0	0	0	0	0	0
14. Your difficulty swallowing at its Worst?	0	0	0	0	0	0	0	0	0	0	0
15. Your coughing at its WORST?	0	0	0	0	0	0	0	0	0	0	0

Page 1 of 2

Copyright 2000 The University of Texas M. D. Anderson Cancer Center All rights reserved.

Date: / (month) Participant Initials: PLEASE USE BLACK INK Participant #:	(day)	\	(year)	Data collection to Assess Acute and Late Normal Tissue Sequelae in Proton Therapy for Adults Protocol: PCR05-0207 Pl: [name] Revision: 05/25/2010									
NOT AS BAD AS YOU CAN IMAGINE 0 1 2 3 4 5 6 7 8 9 10													
16. Your skin pain/burning/rash at it WORST?		0	0	0	0	0	0	0	0	0	0		
17. Your constipation at its WORST	[?] O	0	0	0	0	0	0	0	0	0	0		
18. Your diarrhea at its WORST?	0	0	0	0	0	0	0	0	0	0	0		
19. Your problem with tasting food a its WORST?	t O	0	0	0	0	0	0	0	0	0	0		
20. Your mouth or throat sores at its WORST?	\circ	0	0	\circ	0	0	0	0	0	0	\circ		
21. Your pain in swallowing at its WORST?	0	0	0	0	0	0	0	0	0	0	0		

Part II. How have your symptoms interfered with your life?

Symptoms frequently interfere with how we feel and function. How much have your symptoms interfered with the following items in the last 24 hours:

		Did not Interfere	7		2	4	F		-			Interfered Completely
_		0	1	2	3	4	5	6	7	8	9	10
22.	General activity?	\circ	0	0	\circ	0	0	0	0	0	\circ	0
23.	Mood?	0	0	0	0	0	0	0	0	0	0	0
24.	Work (including work around the house)?	0	0	0	0	0	0	0	0	0	0	0
25.	Relations with other people?	0	0	0	0	0	0	0	0	0	0	0
26.	Walking?	0	0	0	0	0	0	0	0	0	0	0
27.	Enjoyment of life?	0	0	0	0	0	0	0	0	0	0	0

Page 2 of 2 Copyright 2000 The University of Texas M. D. Anderson Cancer Center All rights reserved.

APPENDIX C: EuroQol (EQ-5D)

MOBILITY

Under each heading, please check the ONE box that best describes your health TODAY

I have no problems in walking about I have slight problems in walking about I have moderate problems in walking about I have severe problems in walking about I am unable to walk about SELF-CARE I have no problems with self-care I have SLIGHT problems washing or dressing myself I have moderate problems washing or dressing myself I have severe problems washing or dressing myself I am unable to wash or dress myself **USUAL ACTIVITIES** (e.g., work, study, housework, family or leisure activities) I have no problems doing my my usual activities I have slight problems doing my usual activities I have moderate problems doing my usual activities I have severe problems doing my usual activities I am unable to do my usual activities

Protocol Version: 05/16/2023 Page 32 of 45

PAIN/DISCOMFORT

I have no pain or discomfort	
I have slight pain or discomfort	
I have moderate pain or discomfort	
I have severe pain or discomfort	
I have extreme pain or discomfort	
Anxiety/Depression	
I am not anxious or depressed	
I am slightly anxious or depressed	
I am moderately anxious or depressed	
I am severely anxious or depressed	
I am extremely anxious or depressed	

Protocol Version: 05/16/2023 Page 33 of 45

- We would like to know how good or bad your health is TODAY
- This scale is numbered from 0 to 100.

Protocol Version: 05/16/2023

- 100 means the best health you can imagine.
 0 means the worst health you can imagine.
- Mark an X on the scale to indicate how your health is TODAY.
- Now, please write the number you marked on the scale in the box below

VOLID LIEALTH TODAY -	
YOUR HEALTH TODAY =	

The best

APPENDIX D: Reportable Adverse Events from CTCAE version 4.03

Cardiac AEs

Adverse Event	1	2	3	4	5				
Myocardial infarction	-	Asymptomatic and cardiac enzymes minimally abnormal and no evidence of ischemic ECG changes	Severe symptoms; cardiac enzymes abnormal; hemodynamically stable; ECG changes consistent with infarction	Life-threatening consequences; hemodynamically unstable	Death				
Definition: A disorder characterized by gross necrosis of the myocardium; this is due to an interruption of blood supply to the area.									
Myocarditis	Asymptomatic with laboratory (e.g., BNP [B-Natriuretic Peptide]) or cardiac imaging abnormalities	Symptoms with mild to moderate activity or exertion	Severe with symptoms at rest or with minimal activity or exertion; intervention indicated	Life-threatening consequences; urgent intervention indicated (e.g., continuous IV therapy or mechanical hemodynamic support)	Death				
Definition: A disorder characterize	ed by inflammation of the muscle t	issue of the heart.							
Palpitations	Mild symptoms; intervention not indicated	Intervention indicated	-	-	-				
Definition: A disorder characterize	ed by an unpleasant sensation of i	rregular and/or forceful beating of	the heart.						
Paroxysmal atrial tachycardia	Asymptomatic, intervention not indicated	Symptomatic; medical management indicated	IV medication indicated	Life-threatening consequences; incompletely controlled medically; cardioversion indicated	Death				
Definition: A disorder characterize originates in the atria.	ed by a dysrhythmia with abrupt or	nset and sudden termination of atr	ial contractions with a rate of 150-	250 beats per minute. The rhythm	disturbance				
Pericardial effusion	-	Asymptomatic effusion size small to moderate	Effusion with physiologic consequences	Life-threatening consequences; urgent intervention indicated	Death				
Definition: A disorder characterized by fluid collection within the pericardial sac, usually due to inflammation.									
Pericardial tamponade	-	-	-	Life-threatening consequences; urgent intervention indicated	Death				
Definition: A disorder characterize	ed by an increase in intrapericardi	al pressure due to the collection of	f blood or fluid in the pericardium.						
Pericarditis	Asymptomatic, ECG or physical findings (e.g., rub) consistent with pericarditis	Symptomatic pericarditis (e.g., chest pain)	Pericarditis with physiologic consequences (e.g., pericardial constriction)	Life-threatening consequences; urgent intervention indicated	Death				
Definition: A disorder characterize	ed by irritation to the layers of the	pericardium (the protective sac ar	ound the heart).						

Protocol Version: 05/16/2023 Page 35 of 45

Gastrointestinal AEs

Adverse Event	1	2	3	4	5
Duodenal fistula	Asymptomatic; clinical or diagnostic observations only; intervention not indicated	Symptomatic; altered GI function	Severely altered GI function; tube feeding, TPN or hospitalization indicated; elective operative intervention indicated	Life-threatening consequences; urgent intervention indicated	Death
Definition: A disorder characterize	ed by an abnormal communication	between the duodenum and anot	ther organ or anatomic site.	T	
Duodenal hemorrhage	Mild; intervention not indicated	Moderate symptoms; medical intervention or minor cauterization indicated	Transfusion, radiologic, endoscopic, or elective operative intervention indicated	Life-threatening consequences; urgent intervention indicated	Death
Definition: A disorder characterize	ed by bleeding from the duodenun	1.	I	T	
Duodenal obstruction	Asymptomatic; clinical or diagnostic observations only; intervention not indicated	Symptomatic; altered GI function	Hospitalization or elective operative intervention indicated; disabling	Life-threatening consequences; urgent operative intervention indicated	Death
	ed by blockage of the normal flow	_			
Duodenal perforation	-	Symptomatic; medical intervention indicated	Severe symptoms; elective operative intervention indicated	Life-threatening consequences; urgent operative intervention indicated	Death
Definition: A disorder characterize	ed by a rupture in the duodenal wa	all.	1	T	
Duodenal stenosis	Asymptomatic; clinical or diagnostic observations only; intervention not indicated	Symptomatic; altered GI function	Severely altered GI function; tube feeding; hospitalization indicated; elective operative intervention indicated	Life-threatening consequences; urgent operative intervention indicated	Death
Definition: A disorder characterize	ed by a narrowing of the lumen of	the duodenum.			
Duodenal ulcer	Asymptomatic; clinical or diagnostic observations only; intervention not indicated	Moderate symptoms; medical intervention indicated; limiting instrumental ADL	Severely altered GI function; TPN indicated; elective operative or endoscopic intervention indicated; limiting self care ADL; disabling	Life-threatening consequences; urgent operative intervention indicated	Death
Definition: A disorder characterize	' ed by a circumscribed, inflammato	ry and necrotic erosive lesion on t	he mucosal surface of the duoder	nal wall.	
Dyspepsia	Mild symptoms; intervention not indicated	Moderate symptoms; medical intervention indicated	Severe symptoms; surgical intervention indicated	-	-
Definition: A disorder characterize heartburn, nausea and vomiting.	ed by an uncomfortable, often pair	nful feeling in the stomach, resulting	ng from impaired digestion. Sympt	oms include burning stomach, bloa	ating,
Dysphagia Definition: A disorder characterize	Symptomatic, able to eat regular diet	Symptomatic and altered eating/swallowing	Severely altered eating/swallowing; tube feeding or TPN or hospitalization indicated	Life-threatening consequences; urgent intervention indicated	Death
Enterocolitis	Asymptomatic; clinical or	Abdominal pain; mucus or blood	Severe or persistent abdominal	Life-threatening consequences;	Death
	diagnostic observations only; intervention not indicated	in stool	pain; fever; ileus; peritoneal signs	urgent intervention indicated	
Definition: A disorder characterize	ed by inflammation of the small an	d large intestines.			
Enterovesical fistula	Asymptomatic; clinical or diagnostic observations only; intervention not indicated	Symptomatic; noninvasive intervention indicated	Severe, medically significant; medical intervention indicated	Life-threatening consequences; urgent intervention indicated	Death
Definition: A disorder characterize	ed by an abnormal communicatior	between the urinary bladder and	the intestine.		
Esophageal fistula	Asymptomatic; clinical or diagnostic observations only; intervention not indicated	Symptomatic; altered GI function	Severely altered GI function; tube feeding, TPN or hospitalization indicated; elective operative intervention indicated	Life-threatening consequences; urgent intervention indicated	Death
Definition: A disorder characterize	ed by an abnormal communication	between the esophagus and ano	ther organ or anatomic site.		
Esophageal hemorrhage	Mild; intervention not indicated	Moderate symptoms; medical intervention or minor cauterization indicated	Transfusion, radiologic, endoscopic, or elective operative intervention indicated	Life-threatening consequences; urgent intervention indicated	Death
Definition: A disorder characterize	ed by bleeding from the esophagu	S.			

Protocol Version: 05/16/2023 Page 36 of 45

	+				
Esophageal necrosis	-	-	Inability to aliment adequately by GI tract; radiologic, endoscopic, or operative intervention indicated	Life-threatening consequences; urgent operative intervention indicated	Death
Definition: A disorder characterize	red by a necrotic process occurring	in the esophageal wall.			
Esophageal obstruction	Asymptomatic; clinical or diagnostic observations only; intervention not indicated	Symptomatic; altered GI function; limiting instrumental ADL	Hospitalization indicated; elective operative intervention indicated; limiting self care ADL; disabling	Life-threatening consequences; urgent intervention indicated	Death
Definition: A disorder characteriz	red by blockage of the normal flow	of the contents in the esophagus.	•	•	
Esophageal pain	Mild pain	Moderate pain; limiting instrumental ADL	Severe pain; limiting self care ADL	-	-
Definition: A disorder characteriz	ed by a sensation of marked disco	omfort in the esophageal region.			
Esophageal perforation	-	Symptomatic; medical intervention indicated	Severe symptoms; elective operative intervention indicated	Life-threatening consequences; urgent operative intervention indicated	Death
Definition: A disorder characteriz	ed by a rupture in the wall of the e	sophagus.			
Esophageal stenosis	Asymptomatic; clinical or diagnostic observations only; intervention not indicated	Symptomatic; altered GI function	Severely altered GI function; tube feeding; hospitalization indicated; elective operative intervention indicated	Life-threatening consequences; urgent operative intervention indicated	Death
Definition: A disorder characteriz	red by a narrowing of the lumen of	the esophagus.			
Esophageal ulcer	Asymptomatic; clinical or diagnostic observations only; intervention not indicated	Symptomatic; altered GI function; limiting instrumental ADL	Severely altered GI function; TPN indicated; elective operative or endoscopic intervention indicated; limiting self care ADL; disabling	Life-threatening consequences; urgent operative intervention indicated	Death
Definition: A disorder characteriz	ed by a circumscribed, inflammato	ory and necrotic erosive lesion on	the mucosal surface of the esopha	igeal wall.	
Esophagitis	Asymptomatic; clinical or diagnostic observations only; intervention not indicated	Symptomatic; altered eating/swallowing; oral supplements indicated	Severely altered eating/swallowing; tube feeding, TPN or hospitalization indicated	Life-threatening consequences; urgent operative intervention indicated	Death
Definition: A disorder characteriz	ed by inflammation of the esophag	jeal wall.			
Fecal incontinence	Occasional use of pads required	Daily use of pads required	Severe symptoms; elective operative intervention indicated	-	-
Definition: A disorder characteriz	ed by inability to control the escap	e of stool from the rectum.			
Flatulence	Mild symptoms; intervention not indicated	Moderate; persistent; psychosocial sequelae	-	-	-
Definition: A disorder characteriz	ed by a state of excessive gas in t	he alimentary canal.			
Gastric fistula	Asymptomatic; clinical or diagnostic observations only; intervention not indicated	Symptomatic; altered GI function	Severely altered GI function; bowel rest; tube feeding, TPN or hospitalization indicated; elective operative intervention indicated	Life-threatening consequences; urgent operative intervention indicated	Death
Definition: A disorder characteriz	ed by an abnormal communication	between the stomach and anothe	er organ or anatomic site.		
Gastric hemorrhage	Mild; intervention not indicated	Moderate symptoms; medical intervention or minor	Transfusion, radiologic, endoscopic, or elective operative intervention indicated	Life-threatening consequences; urgent intervention indicated	Death
Definition: A disorder characterist	and by blooding from the gestric wa	cauterization indicated		'	
	ed by bleeding from the gastric wa	1	1		D#
Definition: A disorder characteriz Gastric necrosis	ed by bleeding from the gastric wa	1	Inability to aliment adequately by GI tract; radiologic, endoscopic, or operative intervention indicated	Life-threatening consequences; urgent operative intervention indicated	Death

Protocol Version: 05/16/2023 Page 37 of 45

		l	l	1		
Gastric perforation	-	Symptomatic; medical intervention indicated	Severe symptoms; elective operative intervention indicated	Life-threatening consequences; urgent operative intervention indicated	Death	
Definition: A disorder characterize	ed by a rupture in the stomach wa	II.	'			
Gastric stenosis	Asymptomatic; clinical or diagnostic observations only; intervention not indicated	Symptomatic; altered GI function	Severely altered GI function; tube feeding; hospitalization indicated; elective operative intervention indicated	Life-threatening consequences; urgent operative intervention indicated	Death	
Definition: A disorder characterize	ed by a narrowing of the lumen of	the stomach.				
Gastric ulcer	Asymptomatic; clinical or diagnostic observations only; intervention not indicated	Symptomatic; altered GI function; medical intervention indicated; limiting instrumental ADL	Severely altered GI function; TPN indicated; elective operative or endoscopic intervention indicated; limiting self care ADL; disabling	Life-threatening consequences; urgent operative intervention indicated	Death	
Definition: A disorder characterize	ed by a circumscribed, inflammato	ory and necrotic erosive lesion on t	the mucosal surface of the stomac	ch.	T	
Gastritis	Asymptomatic; clinical or diagnostic observations only; intervention not indicated	Symptomatic; altered GI function; medical intervention indicated	Severely altered eating or gastric function; TPN or hospitalization indicated	Life-threatening consequences; urgent operative intervention indicated	Death	
Definition: A disorder characterize	ed by inflammation of the stomach		I	I		
Gastroesophageal reflux disease	Mild symptoms; intervention not indicated	Moderate symptoms; medical intervention indicated	Severe symptoms; surgical intervention indicated	-	-	
	ed by reflux of the gastric and/or d esult in injury to the esophageal m			nd usually caused by incompetend	e of the lower	
Gastrointestinal fistula	Asymptomatic; clinical or diagnostic observations only; intervention not indicated	Symptomatic; altered GI function	Severely altered GI function; tube feeding, TPN or hospitalization indicated	Life-threatening consequences; urgent operative intervention indicated	Death	
Definition: A disorder characterize	ed by an abnormal communication	between any part of the gastroin	testinal system and another organ	or anatomic site.		
Gastrointestinal pain	Mild pain	Moderate pain; limiting instrumental ADL	Severe pain; limiting self care ADL	-	-	
Definition: A disorder characterize	ed by a sensation of marked disco	mfort in the gastrointestinal region	1.			
Nausea	Loss of appetite without alteration in eating habits	Oral intake decreased without significant weight loss, dehydration or malnutrition	Inadequate oral caloric or fluid intake; tube feeding, TPN, or hospitalization indicated	-	-	
Definition: A disorder characterize	ed by a queasy sensation and/or the	ne urge to vomit.				
Upper gastrointestinal hemorrhage	Mild; intervention not indicated	Moderate symptoms; medical intervention or minor cauterization indicated	Transfusion, radiologic, endoscopic, or elective operative intervention indicated	Life-threatening consequences; urgent intervention indicated	Death	
Definition: A disorder characterized by bleeding from the upper gastrointestinal tract (oral cavity, pharynx, esophagus, and stomach).						
Vomiting	1 - 2 episodes (separated by 5 minutes) in 24 hrs	3 - 5 episodes (separated by 5 minutes) in 24 hrs	>=6 episodes (separated by 5 minutes) in 24 hrs; tube feeding, TPN or hospitalization indicated	Life-threatening consequences; urgent intervention indicated	Death	
Definition: A disorder characterize	ed by the reflexive act of ejecting t	he contents of the stomach through	h the mouth.			
Gastrointestinal disorders - Other, specify	Asymptomatic or mild symptoms; clinical or diagnostic observations only; intervention not indicated	Moderate; minimal, local or noninvasive intervention indicated; limiting age- appropriate instrumental ADL	Severe or medically significant but not immediately life- threatening; hospitalization or prolongation of existing hospitalization indicated; disabling; limiting self care ADL	Life-threatening consequences; urgent intervention indicated	Death	

Metabolism and Nutrition AEs

	Anorexia	Loss of appetite without alteration in eating habits	Oral intake altered without significant weight loss or malnutrition; oral nutritional supplements indicated	_	Life-threatening consequences; urgent intervention indicated	Death
	Definition: A disorder characteri	zed by a loss of appetite.				
diminished skin turgor	Dehydration	dry mucous membranes;	IV fluids indicated <24 hrs		Life-threatening consequences; urgent intervention indicated	Death

Protocol Version: 05/16/2023 Page 38 of 45

Respiratory, Thoracic and Mediastinal AEs

	T.				
Bronchial fistula	Asymptomatic; clinical or diagnostic observations only; intervention not indicated	Symptomatic; tube thoracostomy or medical management indicated; limiting instrumental ADL	Severe symptoms; limiting self care ADL; endoscopic or operative intervention indicated (e.g., stent or primary closure)	Life-threatening consequences; urgent operative intervention with thoracoplasty, chronic open drainage or multiple thoracotomies indicated	Death
Definition: A disorder characterize	ed by an abnormal communication	between the bronchus and anoth	ier organ or anatomic site.		
Bronchial obstruction	Asymptomatic; clinical or diagnostic observations only; intervention not indicated	Symptomatic (e.g., mild wheezing); endoscopic evaluation indicated; radiographic evidence of atelectasis/lobar collapse; medical management indicated (e.g., steroids, bronchodilators)	Shortness of breath with stridor, endoscopic intervention indicated (e.g., laser, stent placement)	Life-threatening respiratory or hemodynamic compromise; intubation or urgent intervention indicated	Death
Definition: A disorder characterize	ed by blockage of a bronchus pass	sage, most often by bronchial secr	retions and exudates.		
Bronchial stricture	Asymptomatic; clinical or diagnostic observations only; intervention not indicated	Symptomatic (e.g., rhonchi or wheezing) but without respiratory distress; medical intervention indicated (e.g., steroids, bronchodilators)	Shortness of breath with stridor; endoscopic intervention indicated (e.g., laser, stent placement)	Life-threatening respiratory or hemodynamic compromise; intubation or urgent intervention indicated	Death
Definition: A disorder characterize	ed by a narrowing of the bronchial	tube.	T		
Bronchopleural fistula	Asymptomatic; clinical or diagnostic observations only; intervention not indicated	Symptomatic; tube thoracostomy or medical intervention indicated; limiting instrumental ADL	Severe symptoms; limiting self care ADL; endoscopic or operative intervention indicated (e.g., stent or primary closure)	Life-threatening consequences; urgent operative intervention with thoracoplasty, chronic open drainage or multiple thoracotomies indicated	Death
Definition: A disorder characterize	ed by an abnormal communication	between a bronchus and the pleu	ural cavity.		
